#### 6.3 **Day 30 ( $\pm 7$ days) Follow-Up Visit**

The subject will be contacted for the following assessments:

- Weight (only required if they have access to a scale and can self-report)
- Medication Review
- Lymphedema Treatment Review
- Arm Girth
- LYMQOL ARM
- SF-36
- LSIDS-A
- Adverse Event (AE) & Device Observation Assessment

#### 6.4 **Day 60 ( $\pm 7$ days) Follow-Up Visit**

The subject will be contacted for the following assessments:

- Weight (only required if they have access to a scale and can self-report)

- Medication Review
- Lymphedema Treatment Review
- Arm Girth
- LYMQOL ARM
- SF-36
- LSIDS-A
- AE & Device Observation Assessment

After the subject has completed their Day 60 follow-up visit, they will be exited from the study and the FT-CC device will be collected. Return of the FT-CC may be done by the subject returning the controller to the clinic or by shipping it back from their home in a box provided by Tactile Medical.

## 6.5 Study Schedule of Activities

The study schedule of activities is shown below (Table 3).

Table 3. Schedule of Study Activities

Assessments	Screening/Baseline	Day 0 - Training	Day 30	Day 60
Visit Window	N/A	Within 21 days after Screening/Baseline	±7 Days	±7 Days
Informed Consent	X			
Demographics & Medical History	X			
Pregnancy Test (if applicable) 	X			
Inclusion/Exclusion Assessment	X			
Height and Weight	X 		X 	X 
Medication Review	X		X	X
Lymphedema Evaluation	X			
Lymphedema Treatment Review	X		X	X
Arm Girth	X		X	X
Randomization	X			
Quality of Life Assessments (LYMQOL ARM, SF-36)	X		X	X
Symptom Assessment (LSIDS-A)	X		X	X
FT-CC Garment Measurements	X			
FT-CC Training		X		
AE & Device Observation Assessment			X	X

If pregnancy test is required, it will be performed in the clinic

Height collected at Screening/Baseline visit only; height and weight collected via self-report for subjects with access to scale or from subject's most recent medical history

Weight collected via self-report if subject has access to a scale at home

## 7.0 Study Procedures

### 7.1 Informed Consent

Subjects will sign an ICF that has been approved by both the Sponsor and reviewing IRB to be considered for participation in this study. Subjects must meet all of the inclusion and none of the exclusion criteria.

Each subject (or a legally authorized representative) must give written consent, in accordance with local requirements, after the nature of the study has been fully explained and all questions answered. The consent form must be signed prior to any study-related procedures, and the process of informed consent must be documented in the medical record, including if the process was performed in-person or remotely.

### 7.2 Demographics & Medical History

Demographics will be collected including the date of birth, ethnicity, race, and sex. Significant medical history, including lymphedema history, will be collected.

### 7.3 Pregnancy Test

Women of childbearing potential will be tested for pregnancy according to the site-specific procedures during the Screening/Baseline visit. If the pregnancy test is positive, the subject will not be enrolled in the study.

### 7.4 Height and Weight

Height and weight will be collected during the Screening/Baseline visit via self-report for subjects who have access to a scale or from the subject's most recent medical history. Weight will be collected during follow-up visits via self-report if the subject has access to a scale.

### 7.5 Medication Review

At each clinic visit, use of the following medications will be documented:

- Beta blockers
- Diuretics
- Oral steroids
- Non-Steroidal Anti-Inflammatory Drugs (NSAIDs)

### 7.6 Lymphedema Evaluation

Research personnel will confirm a diagnosis of unilateral breast cancer-related lymphedema by review of the subject's medical records.

### 7.7 Lymphedema Treatment Review

During each visit, with the exception of the training visit, the subject will also be asked questions regarding their use in the last 7 days of the FT-CC (Day 30 and 60 only), compression garments, and other prescribed lymphedema treatment.

### 7.8 Arm Girth

The subject will be provided with a tape measure to make an arm girth measurement on the anterior forearm 6 cm below the midline of the antecubital fossa on the affected arm (see Figure 2). If a family member or care provider is able to do this measurement for the subject, the same person should perform the measurement at all visits.

[figure not shown]

Figure 2. Arm girth to be measured on the anterior forearm 6 cm below (distal to) the midline of the antecubital fossa.

## 7.9 Randomization

If the subject meets all of the inclusion criteria and none of the exclusion criteria, they will be randomly assigned to ACTIVE FT-CC or PASSIVE FT-CC.

Randomization will occur via entering the randomization CRF in the EDC system. The randomization assignment should not be shared with the research subject.

The randomization assignment cannot be changed or chosen by the subject or the investigator.

## 7.10 Quality of Life Assessments

### 7.10.1 LYMQOL ARM

The LYMQOL ARM is an assessment tool designed for measuring quality of life (QoL) in patients with upper limb lymphedema. It is a 21-item questionnaire which has been designed and validated in patients with chronic edema and covers four domains: function, appearance, symptoms, and mood, and in addition, has an overall QoL score (11). The subject will have a unique user account and can complete the assessment online via secure connection to the study database. If subject is not able to complete the questionnaire electronically, they can also be mailed to them for completion.

### 7.10.2 SF-36

The SF-36 is an assessment of functional status and quality of life. This questionnaire is a validated QoL tool that has been widely utilized and has

been found to be appropriate for use in evaluating health related quality of life impacts. The SF-36 consists of 36 questions that evaluate eight health concepts including physical functioning, role functioning-physical, bodily pain, general health, vitality, social functioning, role functioning – emotional, and mental health.

#### 7.11 **Symptom Assessment**

The LSIDS-A is a 30-item validated assessment tool designed for measuring arm lymphedema and its associated symptoms in patients with breast cancer-related lymphedema (12). The subject will have a unique user account and can complete the assessment online via secure connection to the study database. If a subject cannot complete the questionnaire electronically, a paper version may be mailed to them for completion.

#### 7.12 **FT-CC Garment Measurements**

The subject's chest, arm inseam, biceps, and hips will be measured to determine the appropriate size for the arm-shoulder and trunk garment.

#### 7.13 **FT-CC Training**

After all baseline assessments have been performed, the subject will be contacted by a Tactile Medical trainer to schedule a training visit on how to use the FT-CC. This training may occur virtually, at the clinic, or in the subject's home. Training may be conducted up to 21 days after the baseline visit.

#### 7.14 **AE & Device Observation Assessment**

AE assessment will occur after randomization and continue throughout the study.

Reportable events, as defined below, will be recorded in the subject's medical record and on the CRFs. All device related AEs will be assessed by the Tactile study team for reporting through the Tactile Medical Complaint System.

##### 7.14.1 **AE**

An adverse event is any untoward medical occurrence in a clinical research study subject which may or may not be related to the use of the medical device under investigation.

Adverse events will be reported to the IRB in accordance with IRB policy.

##### 7.14.2 **Serious Adverse Event (SAE)**

A serious adverse event is an untoward medical occurrence where the outcome is:

- Death;
- Life-threatening event (places the subject at immediate risk of death from the experience as it occurred);
- Hospitalization (initial or prolonged) if admission to hospital was warranted as a result of an adverse event;

- Disability or permanent damage (substantial disruption of one's ability to carry out normal life functions);
- Congenital anomaly or birth defect;
- Required intervention to prevent permanent impairment or damage; or
- Important medical event that required medical or interventional treatment to prevent one of the previous outcomes.

Investigators must report all Serious Adverse Events (SAEs) to Tactile Medical within 10 working days of becoming aware of the event. SAEs will be summarized in writing and reported to the IRB in accordance with IRB policy.

#### 7.14.3 Unanticipated Adverse Device Effect (UADE)

A UADE is a serious adverse effect on the health or safety or any life-threatening problem or death caused by, or associated with, a device, if that effect, problem, or death was not previously identified in nature, severity, or degree of incidence in the product labeling, published literature, or Investigational Plan, or any other unanticipated serious problem associated with a device that relates to the rights, safety, or welfare of subjects.

Investigators must report all UADEs to Tactile Medical within 10 working days of becoming aware of the event. UADEs will be summarized in writing and reported to the IRB in accordance with IRB policy.

#### 7.14.4 Device Observations

Device observations will be recorded and reported to Tactile Medical and assessed by the Tactile study team for reporting through the Tactile Medical Complaint system.

#### 7.14.5 Adverse Event Severity

Severity will be assessed by the investigator using the following definitions:

- Mild: Subject aware of sign of symptom, but easily tolerated.
- Moderate: Interferes with normal activities.
- Severe: Incapacitating, with inability to perform normal activities.

### 8.0 Accountability

The FT-CC and FT garments will be provided at no cost to the subject and be utilized with the assistance of study personnel. The FT-CC and FT garments will be shipped directly to the subject and will be returned to Tactile Medical upon study exit. The subject may ship the controller back to Tactile Medical (Tactile Medical will provide a box and label) or return the FT-CC to the site. Tactile Medical will provide all shipping records to the site to enable appropriate accountability of study devices. The record will include the receipt, location, use, and final disposition of all controllers and garments. Subjects may keep the FT garments at the end of the study. Study devices will be stored in a secure area with

restricted access. At the conclusion of the study all FT-CCs will be returned to Tactile Medical.

## 9.0 Risk Analysis

This study does not present risks above and beyond those normally associated with the use of the Flexitouch Plus.

Theoretically, massage and mechanical compression could mobilize dormant tumor cells in some patients; however, this is expected to have limited impact on prognosis such that the benefits of reduction in morbid edema will likely outweigh those theoretical risks.

Pneumatic compression is a minimal risk therapy with nominal complications or adverse events. Known reactions to sequential pneumatic compression therapy include:

Likely:

- Local skin irritation
- Pain or discomfort
- Increased swelling

Less Likely:

- Cellulitis
- New or increased edema in the trunk and/or genital region

Highly Unlikely:

- Electric shock (if device is not maintained or used properly)

Risk analysis assessments determined the probability of occurrence for these potential device risks are at the lowest level. Thus, the residual risks for these types of hazards is acceptable with the benefits to treating patients outweighing the risks.

Use of the Flexitouch Plus may not improve lymphedema symptoms, such as:

- Increased edema
- Pain or discomfort
- Redness, swelling/inflammation, and blistering
- Skin breakdown, including pressure ulcers
- Cellulitis infection
- Stasis dermatitis

The addition of cellular connectivity does not introduce any new risks to the patient regarding treatment. Risk is limited to a potential cybersecurity breach given its cellular connection; however, the device data that is being transmitted does not contain any protected health information (PHI).

If the subject is randomized to the FT-CC arm, they must consent to receiving text messages from Tactile Medical. The text messages will not include any of the subject's PHI.

Subjects will be made aware of known complications and adverse events at the time of consent and monitored closely throughout the study. Subjects will be informed of any significant new findings that develop during the course of the study that may affect their willingness to continue participation. Should a subject choose to terminate his or her

participation in the study, he or she will be treated according to the standard of care that applies at the point of withdrawal.

The Principal Investigator and the study team will oversee all safety aspects and report adverse events to the IRB, as required. Should a subject choose to terminate his or her participation, he or she will be treated according to the standard of care that applies at the point of withdrawal.

## **10.0 Provisions to Protect the Privacy of Study Participants/Information Security Plan**

The most likely risk posed to participants would be a breach of confidentiality if someone other than the research team obtained access to the data.

There are security measures in place to prevent a breach of confidentiality from happening including a password protected electronic database and the use of subject codes to de-identify data.

Precautions will be taken to make sure that only authorized individuals will be accessing subject research records. The collection of sensitive information about subjects is limited to the amount necessary to achieve the aims of the research study, so that no unneeded sensitive information is being collected.

## **11.0 Deviations from Study Plan**

All deviations will be documented and reported to the IRB as required by IRB policies.

## **12.0 Regulatory Assessment**

The investigational device used in this study meets the requirements of a nonsignificant risk (NSR) device given the FT-CC is used for its intended purpose and:

- Is not an implant
- Is not used to support or sustain human life
- Is not of substantial importance in diagnosing, curing, mitigating, or treating disease or otherwise preventing impairment of human health
- Does not otherwise present a potential for serious risk to the health, safety, or welfare of a subject

Per 21 CFR 812, an NSR study is not required to follow all IDE regulations nor have an IDE application approved by FDA before proceeding. An NSR study must follow the abbreviated requirements at 21 CFR 812.2(b) which address labeling, IRB approval, informed consent, monitoring, records, reports, and prohibition against promotion. There is no need to make progress reports or final reports to FDA. In addition, Sponsors and IRBs do not have to report the IRB approval of an NSR device study to FDA. The IRB serves as the FDA's surrogate for review, approval, and continuing review of the NSR device studies. The IRB application should state that the study is NSR and be supported with the rationale in the preceding paragraph. An NSR device study may start as soon as the IRB reviews and approves the study, without prior approval by FDA.

Importantly, the investigational software present on the FT-CC was built in accordance with 820.30 Design Controls, with the controller and garments being manufactured in full compliance with 21 CFR 820.

## **13.0 Quality Assurance Procedures**

This study will be conducted in accordance with Good Clinical Practice (GCP), CFR, institutional research policies and procedures, and other appropriate regulatory requirements to ensure subject safety and quality of clinical procedures related to the conduct of the clinical study. As required by 21 CFR 56 and the Declaration of Helsinki, the protocol, amendments, and ICF will be reviewed and approved, according to 21 CFR §50 and §56, by each center's IRB. This investigational device meets the requirements of a nonsignificant risk (NSR) device; therefore, the study will follow the abbreviated requirements of 21 CFR 812.2(b).

### **13.1 Site Qualification**

Tactile Medical personnel will conduct a Qualification Visit onsite or by telephone to verify the resources, staffing, and subject pool are adequate to ensure successful enrollment and study completion.

### **13.2 Site Initiation**

Tactile Medical personnel will conduct a Site Initiation Visit onsite or by telephone to ensure all required regulatory documents are accurate and complete, and site personnel have been adequately trained on the protocol. An activation letter will be sent to the Principal Investigator once the site is approved to enroll subjects.

### **13.3 Monitoring**

Clinical sites will be monitored, remotely or onsite, for compliance with the clinical protocol, investigator agreement, and applicable regulations throughout the study. Prior to each visit, the investigator will receive a confirmation letter outlining the scheduled dates and activities.

Regular site contact will be maintained to ensure:

- Subject safety;
- Clinical staff are informed of regulations and sponsor requirements;
- The clinical protocol is followed;
- Data is gathered in a complete and timely manner;
- Problems with data or data collection are addressed appropriately and in a timely manner;
- Adverse events are properly reported in a timely manner; and
- Each onsite visit is recorded on the Site Visit Log.

After each visit, the investigator will receive a follow-up letter summarizing site progress as well as any outstanding items that need to be addressed.

In addition to monitoring visits, a screening log must be submitted to Tactile Medical as requested (by fax or e-mail). This screening log should be reviewed with site staff to assess planned versus actual recruitment.

The Principal Investigator and Institution agree to permit study related monitoring, audits, IRB review, and regulatory inspection(s); providing direct access to source data and documents, as appropriate. Monitoring and source verification will be performed by a Tactile Medical clinical research associate (CRA) and/or designee.

Source verification includes reviewing subject source documentation and Case Report Forms (CRFs) for accuracy, completeness, and compliance with GCP.

#### 13.4 **Data Safety Monitoring**

The Principal Investigator (PI) will be responsible for the monitoring of study data and subject safety. Due to the small number of research subjects, the most comprehensive and effective method of monitoring will be an individual case review by the PI and clinical investigators. As this has always been the policy of the PI, the researchers and study team are under specific instructions to make the PI aware of all adverse events, expected or unexpected; therefore, the responsibility for reporting adverse events is shared with the PI and the research team.

Additionally, a periodic review may be completed by a designated member of the Sponsor's Scientific Advisory Board. The frequency of the review will be determined on a number of parameters including, but not limited to: the rate of enrollment, number of AEs and/or SAEs, and number of significant deviations from the protocol. At the conclusion of the review, the reviewer may provide recommendations pertaining to study continuation, modification, or termination of the study or investigational site.

#### 13.5 **Reports and Records**

Records to be maintained by the investigator in a designated study file include:

- Investigational plan and all amendments;
- Signed Investigator Agreement/Research Contract;
- IRB approval letter, including a copy of the approved consent forms, progress reports, and adverse event reports;
- IRB roster or Assurance number, if applicable;
- All correspondence relating to the conduct of this study between the site and sponsor, IRB, and study monitor;
- Curriculum Vitae and professional license for all study personnel, if applicable;
- Financial Disclosure for all Investigators, if applicable;
- Site personnel signature and documentation regarding the investigator's delegation of responsibility;
- Site visit log;
- Protocol/device related training records for all applicable study personnel;
- Device accountability log;
- Device observations;
- Screening log; and
- Reports (shown below).

The Principal Investigator is required to prepare and submit to Tactile Medical, or its designees, complete, accurate, and timely reports on this investigation as required by regulations (Table 6).

Table 6. Required Reports

Reports	Submit To	Timeframe
SAE or UADE	Sponsor and Reviewing IRB	Sponsor: Within 10 working days of becoming aware of the event; IRB: In accordance with IRB procedure.
Withdrawal of IRB Approval	Sponsor	Within 5 working days
IRB determination that study is classified as Significant Risk (SR)	Sponsor	Immediately upon notification from the IRB
Progress	Sponsor and Reviewing IRB	Annually, at a minimum
Final	Sponsor and Reviewing IRB	Within 3 months following the completion or termination of the Investigator's part

The following records must be maintained for each subject enrolled:

- Original, signed and dated ICF, as well as documentation of the process of consent;
- Completed CRFs, DCFs, and source document worksheets, as applicable; and
- Complete medical records including procedure reports, lab reports, etc., as applicable

Subject study records, correspondence files, all supporting study documentation, and reports must remain on file at the site for a minimum of ten years after the conclusion of this study. All investigators must contact Tactile Medical personnel prior to destroying or archiving off-site any records and reports pertaining to this study to ensure that they no longer need to be retained on-site. Additionally, Tactile Medical personnel must be contacted if the investigator plans to leave the investigational site to ensure that arrangements for a new investigator or records transfer are made prior to the investigator's departure.

## 15.0 Changes to Investigational Plan

Should changes in the study plan or protocol become necessary during the course of the clinical research study, proposed changes will be appropriately reviewed and approved by Tactile Medical personnel and the investigator, and IRB approval will be obtained before any changes are implemented. All changes must be documented.

## 16.0 Statistical Methods

### 16.1 Sample Size Determination

No power calculations were used to derive a sample size for this study given this study seeks to identify which health outcomes should be used for a larger randomized controlled trial in the future. The desired target sample size for this feasibility study is 10 analyzable data sets for each group. It is estimated that up to 30 subjects will need to be enrolled to achieve 60 day follow-up data on 20 subjects.

## 16.2 Statistical Analysis

For continuous variables, descriptive statistics will include the number of subjects (n), mean, standard deviation, median, inter-quartile range, minimum, and maximum, based upon subjects with reported data for the variable being analyzed. Frequencies (numerator and denominator), percentages, and 95% confidence intervals will be displayed for categorical data. Percentages by categories will be based on the number of subjects with no missing (unreported) data for the specific variable being analyzed and the count of the patients for each individual level of the categorical variable (the level specific numerators). Percentages will add up to 100%, unless otherwise indicated.

There are no plans to impute missing data and there are no plans to explicitly report missing data (counts and/or percentages) in the tables for all variables as part of the planned study report content. Variations in the reported sample sizes within and/or between relevant tables can be used to ascertain insights into unreported data. In some cases, unreported data may be the result of it not being clinically relevant to a particular patient or may represent expected data that was not collected. Selected analyses pertaining to unreported and/or missing data may be discussed and considered as future findings warrant.

The feasibility nature of the study suggests that the statistical focus will be on estimation and hypothesis generation. Thus, formal statistical tests of hypotheses are not planned.

All data processing, summarization, and analyses will be performed using R Version 3.6.0 or higher.

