### 5.1.3 Outcome Measures

Primary and exploratory endpoints will be based on the outcome measures as described in Table 2.

Table 2. Outcome Measures

Endpoint	Outcome Measure
Compliance	
 
• Compare rate of compliance (# of days used/total study days) to prescribed treatment between FT-CC PASSIVE and FT-CC ACTIVE Subjects at 30 and 60 days
 

Change in Arm Girth	
 
• Comparison between baseline and day 30/60 arm girth measurement
 

Quality of Life	
 
• Comparison between baseline, 30 day, and 60 day surveys
 

Symptom Assessment	
 
• Comparison between baseline, 30 day, and 60 day surveys
 

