#### **5.4 Subject Discontinuation or Withdrawal**

Subject participation may be discontinued prior to study completion for any of the following reasons:

- **Withdrawal of Consent**  
Subjects may withdraw their consent to participate at any time. If a subject withdraws consent, previous information that has already been obtained will be available for analysis.
- **Discretion of the Principal Investigator**

Subjects may be withdrawn at the investigator's discretion in the event of changes in the subject's health, or other reasons based on the investigator's clinical judgment.

When a subject withdraws prior to completing the study, the reason for withdrawal will be recorded.

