#### **5.5 Randomization Assignment and Treatment Duration**

Eligible patients will be randomized (1:1) to one of the following groups for 60 days:

- ACTIVE FT-CC – Text message reminders will be sent if subject does not use device for 2 consecutive days
- PASSIVE FT-CC – Text message reminders will not be sent to subjects

The FT-CC prescription will be a daily 60-minute U1 unilateral treatment at normal pressure. Settings and programs may be modified by the discretion of the investigator, if needed, and these modifications will be documented. If subjects are assigned to the ACTIVE FT-CC group and their device is not used for 2 consecutive days, they will receive a text message reminding them to use their device. If subjects are assigned to the PASSIVE FT-CC group, they will not receive text message reminders.

If subjects assigned to the ACTIVE FT-CC group are not able to receive text messages due to cellular connectivity or text transmission issues, alternate methods may be used to remind the subject to use their device and will be documented on the Case Report Form (CRF).

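### Does the compliance rate need a fixed scoring rule for subjects who withdraw or exit off Day 60?

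*Combined protocol and SAP*

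**What the plan says.** Table 2 in section 5.1.3 gives the primary measure: "Compare rate of compliance (# of days used/total study days) to prescribed treatment", by arm, at 30 and 60 days. Section 5.5 sets the period: "Eligible patients will be randomized (1:1) to one of the following groups for 60 days". Training is labelled Day 0 in section 6.2 and in Table 3, and it may fall up to 21 days after the baseline visit at which randomisation takes place. The Day 30 and Day 60 visits each have a window of ±7 days. Section 6.4 ties exit to the visit and not to the calendar day: "After the subject has completed their Day 60 follow-up visit, they will be exited from the study and the FT-CC device will be collected".

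On who is analysed, section 16.2 describes continuous variables "based upon subjects with reported data for the variable being analyzed" and adds: "There are no plans to impute missing data and there are no plans to explicitly report missing data (counts and/or percentages) in the tables". The same section reports n for each continuous summary, says that differences in sample size give insight into unreported data, and leaves room for selected missing-data analyses. It plans no formal hypothesis tests.

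Section 5.4 says of a subject who withdraws consent that "previous information that has already been obtained will be available for analysis", and it requires the reason for any withdrawal to be recorded. Section 16.1 gives the recruitment aim: "The desired target sample size for this feasibility study is 10 analyzable data sets for each group", and "It is estimated that up to 30 subjects will need to be enrolled to achieve 60 day follow-up data on 20 subjects".

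**The concern.** The outcome is device use, so leaving the study and using the device little are plausibly linked. The treatment of withdrawals is therefore part of the endpoint. Three readings seem open: completers only (suggested by the target in section 16.1), all subjects over their own days, or all subjects over a fixed 30 and 60 days.

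Because the device transmits its use (section 3.2), a woman who leaves at day 20 has real use data. The plan does not say whether she has reported data for the 60-day rate. If she used the device daily, she scores 100% over her own days or 33.3% over 60, or she is left out.

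If withdrawals differ between arms in number, timing or prior use, the choice of reading can hide, create or reverse an arm difference. Nothing in the text prevents that choice from being made after the data are seen. At stake is the primary estimate of a study whose purpose is estimation for a larger trial.

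**Working it through.** **The plan's own figure.** Section 16.1 goes from 20 subjects with 60-day data to up to 30 enrolled. No dropout rate is stated. Solving back, 1 − 20/30 = 33.3%, and 20/(1 − 1/3) = 30. The match is an identity and not a check. It shows that up to 10 of 30 may lack 60-day data. This is a planning ceiling, and the plan does not say that all 10 would be withdrawals.

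**Which readings the text supports.** The available-case rule in 16.2 and the retention of obtained data in 5.4 both favour keeping withdrawn subjects. Section 16.1 sets a sample-size target, not an analysis rule, so completers-only is the weakest reading. Since training is Day 0, the natural clock runs from training to Day 30 and Day 60. The open question is mainly own days versus fixed days.

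**Effect on an arm mean.** The documents give no use or withdrawal rates, so all inputs here are assumed except 15 per arm (30 subjects, 1:1). Completers use the device on c = 70% of days. L subjects withdraw after using it on w = 50% of days to day s = 20.

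- Completers only: c = 70%, whatever L is.
- Own days: ((15 − L)c + Lw)/15. Each withdrawal lowers the mean by (0.70 − 0.50)/15 = 1.3 points.
- Fixed 60: ((15 − L)c + Lw·s/60)/15. Each withdrawal lowers it by (0.70 − 0.50 × 20/60)/15 = 3.6 points.

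Arm differences when use is otherwise identical, in points:

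| Withdrawn | Completers | Own days | Fixed 60 |
|---|---|---|---|
| 1 vs 3 | 0 | 2.7 | 7.1 |
| 3 vs 7 | 0 | 5.3 | 14.2 |
| 5 vs 5, same timing | 0 | 0 | 0 |
| 5 vs 5, leaving day 40 vs day 10 | 0 | 0 | 8.3 |

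**Sensitivity of the per-withdrawal shift.** With w from 30% to 70% and s from day 10 to day 40, the shift is 0 to 2.7 points (own days) and 1.6 to 4.3 points (fixed 60). Those limits follow from the grid. With w = 90% to day 50, the shifts are (0.70 − 0.90)/15 = −1.3 and (0.70 − 0.90 × 50/60)/15 = −0.3. The direction is therefore not fixed.

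**Equal losses when the arms do differ.** Take completers at 80% vs 70%, 5 vs 5 withdrawn, and identical withdrawers in both arms. Completers-only gives +10.0. Own days and fixed 60 both give (10 × 80 − 10 × 70)/15 = +6.7. Equal loss leaves the difference unchanged in the table only because completers there are equal as well.

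**Reversal.** Suppose each arm has 10 subjects at 70% and 5 at 20%, and only the five low users in ACTIVE leave, at day 20. PASSIVE is (10 × 70 + 5 × 20)/15 = 53.3%. ACTIVE is 70.0% (completers), 53.3% (own days) or (10 × 70 + 5 × 20 × 20/60)/15 = 48.9% (fixed 60). The differences are +16.7, 0 and −4.4. This case is constructed as an extreme.

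**Visit window.** 42 days used with exit on Day 53 is 42/53 = 79.2% or 42/60 = 70.0%. 45 days used by Day 60, none after, and exit on Day 67 is 45/67 = 67.2% or 45/60 = 75.0%. One such subject moves a 15-subject mean by 9.2/15 = 0.6 or 7.8/15 = 0.5 points.

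**Yardstick.** With an assumed between-subject SD of 25 to 30 points, the standard error of the arm difference is SD × √(2/15) = 9.1 to 11.0 points. The 14.2-point shift is 1.3 to 1.6 standard errors, the 5.3-point shift is 0.5 to 0.6, and one excess withdrawal on fixed 60 is 0.3 to 0.4.

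**The case for a change.** The best case for a change is that this is the primary endpoint and a few sentences would define it. Reported sample sizes do not reliably expose the problem: under own-days or fixed-day scoring a withdrawn subject still counts in n, and n shows neither timing nor reason. The ambiguity also carries into the categories in Table 1. A daily user who leaves at day 20 averages 7 days a week over her own days but 20/60 × 7 = 2.3 over 60 days, so she changes category.

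Most of this stands as description. The denominator is unspecified for these subjects, and a confirmatory trial would have to fix it. What does not stand is the step from an unstated choice to an error. The large shifts need strong assumptions: 3 vs 7 uses the whole ceiling of 10 as withdrawals and loses 47% of one arm, and the reversal above needs 5 vs 0, all of them the lowest users.

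Nor does one scoring rule dominate. Fixed-day scoring counts a withdrawal for health reasons, which section 5.4 allows for, as non-use. Own-days scoring gives full credit to someone who stops early. Prescribing either would replace an open choice with a debatable one.

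**Conclusion.** The gap exists, but it is missing detail and not a fault in a rule the plan states. Under the assumed inputs it is worth about 1.3 points (own days) or 3.6 points (fixed 60) per withdrawal by which the arms differ. With an imbalance of four it reaches 5.3 or 14.2 points. The visit window adds 0.5 to 0.6 points per affected subject.

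No change follows, for three reasons.

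- The plan's formula, its available-case rule and its retention of data after withdrawal lead an analyst to keep withdrawn subjects and count from Day 0, with only the denominator left to state.
- The choice does not affect what is collected. Use is transmitted and withdrawal reasons are recorded, so either scoring, or both, can be produced at reporting.
- The study is descriptive, with up to 30 subjects, no power calculation and no tests. An analyst's choice here cannot inflate a type I error or support a confirmatory claim.

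The conclusion assumes that usable day-level records survive withdrawal. The reminder trigger of two consecutive days without use implies such records. It also assumes that the report says which denominator was used. The plan does not require that statement, but without it the rate could not be interpreted.
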